5.3 Secondary Efficacy Analyses

5.3.1 Percent change from baseline in UPCR during the 26 Week placebo-controlled treatment period

Urinary protein:creatinine ratio (UPCR) is computed at Baseline, Weeks 1, 2, 4, 12, 20, 26 during the 26 week double-blind treatment period and Weeks 28, 32, 38, 52 and 60 during the active treatment and follow-up periods.

5.3.1.1 Primary Analysis

The primary analysis will be based on the ITT population in the elevated C5b-9 stratum (>244 ng/ml). The primary analysis of percent change from baseline (in the form of ratio) in UPCR over 26 weeks will be performed in the subjects in ITT population whose UPCR is abnormal at baseline using a mixed effect model for repeated measures (MMRM) analysis with treatment group, visit, treatment-by-visit interaction and baseline as a covariate. The abnormal UPCR value is defined as UPCR ≥ 0.15 g/g. Subjects will be considered as repeated measure units over visits. Point estimates and corresponding 95% confidence intervals will be estimated for the difference between avacopan and placebo across 26 weeks using a simple contrast from the model.

To alleviate the skewness of the data, UPCR will be log_e-transformed before entering into the MMRM analysis. Least squares mean differences between avacopan and the placebo group in the percent change from baseline to Week 26 log(UPCR) will be back transformed to obtain the estimate for the baseline-adjusted reduction from control in UPCR. Corresponding P-values will also be presented.

In the MMRM model, missing data will not be imputed. Toeplitz covariance matrix will be used to model within-subject variance-covariance structure for the model errors. If the model does not converge using the Toeplitz covariance matrix, AR(1) covariance matrix will be used. If convergence is still not met, then compound symmetry (CS) will be used.

The code used to generate the MMRM analysis will be similar to the following:

```
Note:
TRT01AN = randomized treatment group (numeric): 1=Placebo, 2=Avacopan
VISITN = Visit Number
LR2BASE = Ratio of Visit Value to Baseline Value (log-transformed)
LBASE = Baseline value of response (log transformed)
proc mixed data=lablog;
class SUBJID VISITN TRT01AN(ref='1');
model LR2BASE = TRT01AN VISITN TRT01AN*VISITN LBASE/
solution cl ddfm=kr;
Repeated VISITN / TYPE=TOEP sub=SUBJID;
**use AR(1) if no convergence, then CS;
lsmeans VISITN*TRT01AN / alpha=0.05 cl pdiff slice=VISITN;
ods output LSMeans=LSM
```

5.3.1.2 Secondary Analysis

run;

The same analysis as described for the primary analysis will also be performed for the following:

- Percent change from baseline over 26 weeks during the double-blind treatment period in the combined C5b-9 strata (subjects with elevated C5b-9 blood levels and non-elevated C5b-9 blood levels)
- Percent change from week 26 to week 28, 32, 38, 44 and 52 by prior treatment group during the Avacopan treatment period in the elevated C5b-9 stratum
- Percent change from week 26 to week 28, 32, 38, 44 and 52 by prior treatment group during the Avacopan treatment period in the combined C5b-9 strata (subjects with elevated C5b-9 blood levels and non-elevated C5b-9 blood levels).

Additionally, percent change from baseline in UPCR across the entire study including visits during the follow-up period (Weeks 54, 57 and Week 60) will be summarized by treatment group. The percent change from baseline to Week 52 in UPCR in the avacopan group will be compared to the percent change from baseline to Week 52 in the placebo control group using similar methodology as described for the primary analysis (ANCOVA) of C3G Histologic Index for disease activity. Missing data will not be imputed. Summary and analyses will be carried out in the ITT population in the elevated C5b-9 stratum (>244 ng/ml) and separately for the combined C5b-9 strata.

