8.7. Statistical Analysis Methodology

A statistical analysis plan (SAP).with specific details of all the planned analyses and sensitivity analyses will be generated and approved before unblinding the data for analysis.

All statistical testing will be two-sided, with the Type I error rate at $\alpha = 0.05$.

The efficacy analyses for the efficacy endpoints will be performed in the ITT and PP populations, with the ITT analysis being the primary analysis.

The earliest timepoint at which the primary analysis of the efficacy endpoints can be conducted is when all patients in the elevated stratum have completed at least the Week 26 study visit. Additionally, enrollment for the stratum with C5b-9 levels ≤ 244 ng/ml could terminate early, if patient enrollment in the other stratum (C5b-9 level > 244 ng/mL) reaches target enrollment first. Further, both strata can be analyzed separately and independently. The stratum with elevated levels (primary population) will be analyzed first should the stratum with C5b-9 ≤ 244 ng/ml (secondary population) continue a blinded follow up – further details will be provided in the SAP.

For efficacy analysis, to control for the Type I error rate, a gate-keeping procedure will be applied for the analysis of the primary efficacy endpoint (percent change in C3G Histologic Index for disease activity). The primary endpoint will be tested in the elevated C5b-9 stratum first with a two-sided $\alpha = 0.05$. If this test reaches statistical significance, then the primary endpoint will be tested in the non-elevated C5b-9 stratum with a two-sided $\alpha = 0.05$. If the test in the elevated stratum fails to reach statistical significance, then the test in the non-elevated C5b-9 stratum will not be performed and only performed as an exploratory analysis. The statistical analysis for the secondary endpoint (C3G Histologic Index for disease chronicity) will be tested at a 0.05 α -level only if the primary endpoint in the same stratum reaches statistical significance.

Another analysis will be performed when all patients have completed the study after week 60. Individual patient group assignment will remain blinded to investigators and patients until after the analysis of the data from the second analysis in order to maintain study integrity.

Baseline is defined as the last value prior to start of dosing with study medication (typically the Day 1 pre-dose value).

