8.8. Sample Size Justification

A sample size of 22 patients per treatment group (avacopan and placebo, respectively) in each of the C5b-9 level strata is based on the between-treatment difference of -35% in the C3G Histologic Index for activity at Week 26, standard deviation (SD) 34%, power 90%, and 2-sided $\alpha = 0.05$.

The sample size of 22 per group also provides approximately 90% power to detect a delta of -35% in the C3G Histologic Index for activity between the percent change from baseline in the first 26 weeks and in the second 26 weeks, assuming an SD of 34% for each change.

The mean treatment effect size of 35% is considered reasonable based of the following:

- Of the 5 patients with histologic data in the study by [Herlitz et al., 2012](#) with eculizumab, an anti-C5 antibody, 2 patients had a 67% decrease (improvement) in histologic score, 1 had a 43% decrease, and 2 had no change from baseline; the mean decrease for the 5 patients was 35%;
- An improvement in the histologic score of at least 35% is considered clinically meaningful by clinical and histology experts;
- The SD for the percent change from baseline in C3G Histologic Index of activity was 34% in the Herlitz study; a change of 35% of greater will be above the observed variance for this parameter.

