5.3.1.4 Sensitivity Analysis

For subjects who had clinical significant increased doses or new introduction of ACE inhibitors/ARB post baseline, a sensitivity analysis will be performed where data is imputed after the point of ACE inhibitors/ARB treatment change. The last observation prior to the start of concomitant medication will be carried forward to subsequent time points. Note that LOCF can only be applied within a treatment period and not across periods. Sensitivity analysis will be carried

out similar to the primary and secondary analyses of UPCR as described in Sections 5.3.1.1 and 5.3.1.2:

- Percent change from baseline to Week 26 during the double-blind treatment period (separately for elevated C5b-9 stratum and combined C5b-9 strata)
- Percent change from Week 26 to Week 52 during the Avacopan treatment period (separately for elevated C5b-9 stratum and combined C5b-9 strata)
- Percent change from baseline across the entire study with comparison between treatments at Week 52 period (separately for elevated C5b-9 stratum and combined C5b-9 strata)

Additional sensitivity analysis of UPCR may be conducted to explore other aspects of changes of ACE inhibitor/ARB treatments for C3G, such as clinical significant dose decreases in Period A.

5.3.2 Change and Percent change from baseline in eGFR during the 26 Week placebocontrolled treatment period

The same analysis as described for UPCR will be carried out for estimated glomerular filtration rate (eGFR) including primary and secondary analyses. eGFR will not be log_e-transformed before entering into the MMRM analysis. eGFR is computed at Baseline, Weeks 2, 4, 12, 20, 26 during the 26 week double-blind treatment period and Weeks 32, 38, 52 and 60 during the active treatment and follow-up period.

A subgroup analysis for the change and percent change from baseline in eGFR will be performed in patients with impaired renal function at baseline eGFR ($<60, \ge 60 \text{ mL/min/1.73 m}^2$), if there are sufficient number of subjects in these subgroups

5.3.3 Change from baseline in the C3G Histological Index for disease chronicity during the 26 Week placebo-controlled treatment period

C3G Histologic Index for disease chronicity considers 4 lesions and can assume a score from 0 to 10. See Section 2.3.4 for further details on the calculation of C3G Histologic Index for disease chronicity.

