9 SAMPLE SIZE AND POWER CONSIDERATIONS

A sample size of 22 patients per treatment group (avacopan and placebo, respectively) in each of the C5b-9 level strata is based on the between-treatment difference of -35% in the C3G

Histologic Index for activity at Week 26, standard deviation (SD) 34%, power 90%, and 2-sided $\alpha = 0.05$.

The sample size of 22 per group also provides approximately 90% power to detect a delta of -35% in the C3G Histologic Index for activity between the percent change from baseline in the first 26 weeks and in the second 26 weeks, assuming an SD of 34% for each change. The mean treatment effect size of 35% is considered reasonable based of the following:

- Of the 5 patients with histologic data in the study by Herlitz et al., 2012 with eculizumab, an anti-C5 antibody, 2 patients had a 67% decrease (improvement) in histologic score, 1 had a 43% decrease, and 2 had no change from baseline; the mean decrease for the 5 patients was 35%;
- An improvement in the histologic score of at least 35% is considered clinically meaningful by clinical and histology experts;
- The SD for the percent change from baseline in C3G Histologic Index of activity was 34% in the Herlitz study; a change of 35% of greater will be above the observed variance for this parameter.

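### The repeated-measures models allow only equal-variance structures, so the Week 26 test and interval for UPCR, eGFR, MCP-1 and quality of life are unprotected if variance grows over visits

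*SAP*

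**What the plan says.** SAP 5.3.1.1 analyses the log ratio of UPCR to baseline with treatment, visit, their interaction and log baseline: "model LR2BASE = TRT01AN VISITN TRT01AN*VISITN LBASE". For the covariance it says that "Toeplitz covariance matrix will be used to model within-subject variance-covariance structure for the model errors", coded as "Repeated VISITN / TYPE=TOEP sub=SUBJID". The fallback depends on convergence only: "If the model does not converge using the Toeplitz covariance matrix, AR(1) covariance matrix will be used", and after that compound symmetry. Degrees of freedom and standard errors are Kenward-Roger. There is no unstructured or heterogeneous option, no robust standard error and no sensitivity analysis of the covariance.

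The model is then reused. For eGFR, SAP 5.3.2 says "The same analysis as described for UPCR will be carried out for estimated glomerular filtration rate (eGFR) including primary and secondary analyses", without the log transform. SAP 5.3.5 and 5.3.6 do likewise for MCP-1:creatinine and for SF-36 v2 and EQ-5D-5L. UPCR and eGFR head the list of secondary endpoints in SAP 2.3.2; MCP-1 and quality of life are other endpoints in 2.3.3.

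The target contrast is described in two ways. SAP 5.3.1.1 first names a treatment difference over the 26 weeks, then back-transforms the difference in change to Week 26. Its code prints treatment-by-visit means and no averaged contrast. Protocol 8.7.5 names Week 26.

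**The concern.** Toeplitz, AR(1) and compound symmetry differ in how they model correlation, but each has a single variance. The standard error at Week 26 therefore comes from a variance pooled over all visits, three of which (for UPCR and MCP-1) fall in the first four weeks. Early changes from baseline are often less variable than late ones, because an early value is usually still close to baseline. If so, the pooled variance understates the Week 26 variance, and the interval there is too narrow. The fallbacks keep the same restriction. Because they are triggered by convergence and not by fit, nothing in the plan would detect or correct it. At stake is whether the reported p-values and 95% intervals for proteinuria and eGFR at the end of the placebo-controlled period mean what they say.

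**Working it through.** **The plan's own figure.** The only sizing in the documents is for histology: difference 35, SD 34, 90% power, two-sided 5%. n = 2 × (1.960 + 1.282)² × 34² / 35² = 19.8, so 20 per arm; the t distribution needs 21. At the planned 22 per arm ("A sample size of 22 patients per treatment group (avacopan and placebo, respectively) in each of the C5b-9 level strata"), power is 91.5% by the t distribution. That figure reproduces and is not in question. No SD, correlation or power is given for any endpoint analysed by the repeated-measures model.

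**Inputs from the documents.** Level: "All statistical testing will be two-sided, with the Type I error rate at" 0.05 (protocol 8.7). Post-baseline visits in the 26-week period: UPCR and MCP-1 at Weeks 1, 2, 4, 12, 20, 26; eGFR at Weeks 2, 4, 12, 20, 26; quality of life at Weeks 4, 12, 20, 26 (SAP 5.3.1, 5.3.5, 5.3.2, 5.3.6).

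**Assumed inputs.** Constant marginal variance (set to 1), and a correlation with baseline, r(t), that decays exponentially between a Week 1 value and a Week 26 value.

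**Formulas.** Residual variance of change given baseline: v(t) = 1 − r(t)². A homogeneous structure uses roughly the mean of v over visits. So SE ratio = √(mean v / v(26)), and size = 2 × [1 − Φ(1.96 × SE ratio)].

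**Strong decay, UPCR, 0.94 to 0.60.** r = 0.940, 0.923, 0.891, 0.772, 0.668, 0.600, giving v = 0.116, 0.148, 0.207, 0.405, 0.553, 0.640. Mean 0.345; SE ratio √(0.345/0.640) = 0.734; size = 2 × [1 − Φ(1.439)] = 15.0%.

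**Mild decay, UPCR, 0.70 to 0.60.** v = 0.510, 0.516, 0.528, 0.572, 0.612, 0.640. Mean 0.563; SE ratio 0.938; size = 2 × [1 − Φ(1.839)] = 6.6%.

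| Correlation, Week 1 to Week 26 (assumed) | UPCR | eGFR | Quality of life |
|---|---|---|---|
| 0.94 to 0.60 | 15.0% | 12.6% | 10.0% |
| 0.89 to 0.70 | 11.3% | 10.0% | 8.5% |
| 0.89 to 0.80 | 9.0% | 8.3% | 7.4% |
| 0.80 to 0.70 | 7.5% | 7.1% | 6.6% |
| 0.70 to 0.60 | 6.6% | 6.4% | 6.0% |
| no decay | 5.0% | 5.0% | 5.0% |

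Using the likelihood-fitted Toeplitz variance in place of the plain mean gives 13.5-14.6% in the first UPCR cell, depending on how the common baseline slope is handled, and moves the other cells by less than one point. AR(1) and compound symmetry are within about 0.6 points of Toeplitz. MCP-1 has the UPCR visit set, so the UPCR column applies to it under the same correlations.

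**Check by fitting the model.** REML fits of the SAP model (22 per arm, complete normal data, Satterthwaite degrees of freedom, 250 fits per scenario, UPCR visits, Toeplitz) gave the following by ratio of Week 26 SD to Week 1 SD:

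| SD ratio | 0.67 | 1.0 | 1.25 | 1.5 | 2.0 | 2.5 |
|---|---|---|---|---|---|---|
| Size at Week 26 | 1.5% | 4.7% | 7.6% | 9.6% | 12.8% | 14.7% |
| Model SE / true SE | 1.25 | 1.01 | 0.90 | 0.84 | 0.77 | 0.74 |

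Other growth shapes reached 15.8%. For the average over visits, size was 2.6-5.1% in every scenario. A last-visit ANCOVA with its own variance, standing in for a visit-specific variance, rejected in about 4.6% of 1,320 null trials.

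**The case against.** The strongest objection is that the size of the problem rests on unseen inputs. A reader might infer that the Week 26 standard error is too small as a matter of fact, and that one inflation figure applies to all four endpoint families. The documents do not support either. They give no SD by visit and no correlation with baseline. UPCR and MCP-1 come from single clean-catch samples (protocol 7.1.2), and short-term noise lowers the Week 1 correlation and flattens the growth. The visit sets also differ: quality of life starts at Week 4 and is less exposed. This objection stands, so the result has to be conditional and given by endpoint.

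A second objection is that the SAP's first description of the contrast could mean an average over 26 weeks, for which there is no inflation, and that the SAP supersedes the protocol. This stands as an ambiguity. It does not remove the point, because the SAP's back-transformed estimate, its visit-by-visit code and protocol 8.7.5 all lead to Week 26.

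Third, a reader might infer a breach of the trial's Type I error control. There is none: the gatekeeping in SAP 3.1 covers the histologic activity index and then chronicity, and none of these endpoints.

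Fourth, an unstructured matrix is demanding with few patients. That is fair, and is why ordered fallbacks are needed.

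**Conclusion.** The specification weakness holds: every permitted structure assumes equal variance across visits, for all four endpoint families, and nothing else in the model protects the Week 26 standard error. The consequence is conditional. Under constant marginal variance and the assumed correlations above, the nominal 5% test at Week 26 runs at about 7-15% for UPCR, 6-13% for eGFR and 6-10% for quality of life, so a nominal 95% UPCR interval would cover about 85-93%. With flat variance it keeps its level, with falling variance it is conservative, and an average over 26 weeks is not inflated. The effect is on nominal p-values and intervals, not on the controlled error rate. The structural point is firm; no single percentage is. The checks assume complete, normal data and, in the simulation, 22 per arm. The UPCR set may be smaller because it requires a baseline of at least 0.15 g/g and the ITT set has its own exclusions (SAP 3.2.2).

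**What to change.** In SAP 5.3.1.1, specify `TYPE=UN` with `ddfm=kr` first; if it does not converge, `TOEPH`, then `ARH(1)` or `CSH`. Keep Kenward-Roger. Uncorrected empirical standard errors are not a good substitute: in a single-visit simulation at 22 per arm a basic sandwich estimator rejected 6.0% (t) to 6.8% (z) of the time. State that the Week 26 contrast is primary, as in protocol 8.7.5, and label any 26-week average as supportive. Carry both changes to SAP 5.3.2, 5.3.5 and 5.3.6. A baseline-by-visit term (`LBASE*VISITN`) is optional, since it cuts Week 26 variance by only 0-4% under the assumed correlations.

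The cost is a few lines of text and code before database lock. With six visits, the unstructured matrix has 6 × 7 / 2 = 21 parameters and heterogeneous Toeplitz has 6 + 5 = 11, against 6 for Toeplitz, in about 44 patients or fewer. Some non-convergence is possible, hence the fallback order, and intervals may be slightly wider.

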5.3.1.3 Subgroup Analysis

A subgroup analysis will be carried out separately based on baseline UPCR (>1 vs ≤ 1 g protein/g creatinine). These analyses will be the same as described in Section 5.3.1.1 for the following:

- Percent change from baseline over 26 weeks during the double-blind treatment for the elevated C5b-9 stratum
- Percent change from baseline over 26 weeks during the double-blind treatment period in the combined C5b-9 strata

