8.7.5. Efficacy Analyses

Summary statistics will be calculated for each of the efficacy endpoints. For categorical endpoints, numbers and percentages, and 95% confidence intervals will be calculated. For continuous variables, numbers, means, medians, minimum, maximum, standard deviations, and standard error of means, and 95% confidence intervals will be calculated. Geometric means will be calculated for UPCR and urinary MCP-1:creatinine, and other data that are not normally distributed.

Results will be presented by treatment group. Results will be presented by stratum for C3GN vs. DDD and renal transplant vs. no renal transplant. Data will also be presented by geographic distribution (North America vs. Rest of World), sex, age group (including a separate analysis in 12-17 year old patients), race, and ethnicity for at least the primary endpoint.

The overall efficacy hypothesis in this study is that avacopan treatment will be effective in treatment of patients with C3G based on improvement in renal histology (C3G histologic index of activity).

The primary efficacy endpoint is the percent change from baseline to Week 26 in the C3G Histologic Index for disease activity.

- The null hypothesis (H_0) is that the avacopan group is not different from the placebo group when comparing the percent change from baseline to Week 26 in the C3G Histologic Index for disease activity.
- The alternative hypothesis (H_1) is that the avacopan group is superior to the placebo group when comparing the percent change from baseline to Week 26 in the C3G Histologic Index for disease activity.

Avacopan and placebo groups will be compared by ANCOVA with treatment group as factor and baseline C3G Histologic Index for disease activity as covariate. A point estimate and corresponding 95% confidence interval will be estimated for the treatment main effect. The heterogeneity of the treatment effect across disease diagnoses and renal transplant strata will be investigated through subgroup analyses. If data are not normally distributed, in addition to the ANCOVA for the percent change in C3G Histologic Index for disease activity and chronicity,

the Cochran-Mantel-Haenszel (CMH) test will be applied to the percent change results and ANCOVA will be applied to the change in C3G Histologic Index disease activity and chronicity scores.

The treatment effect based on the baseline complement profile of patients will also be investigated.

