5.2 Primary Efficacy Analysis

The primary efficacy endpoint is the percent change from baseline to Week 26 in the C3G Histologic Index for disease activity. The C3G Histologic Index for disease activity can assume a score from 0-21. See Section 2.3.4 for further details on the calculation of C3G Histologic Index for disease activity.

Statistical Hypothesis Testing and Procedure

• The null hypothesis (H0) is that the avacopan group is not different from the placebo group when comparing the percent change from baseline to Week 26 in the C3G Histologic Index for disease activity.

• The alternative hypothesis (H1) is that the avacopan group is different from the placebo group when comparing the percent change from baseline to Week 26 in the C3G Histologic Index for disease activity.

Numbers, means, median, standard deviation, standard error of means, minimum and maximum will be presented by treatment group and study visit. Avacopan and placebo groups will be compared by Analysis of Covariance (ANCOVA) with treatment group as factor and baseline C3G Histologic Index for disease activity as a covariate. The LS mean estimate and corresponding 95% confidence interval (CI) will be estimated for the treatment main effect. The heterogeneity of the treatment effect across disease diagnoses and renal transplant strata may be investigated through subgroup analyses.

As there are no data available to access the possibility of non-normality distribution of percent change or change from baseline, normality distribution tests will be performed for both percent change and change from baseline. It is possible that the normality test would not hold for percent change from baseline or change from baseline or both. In this case, the following is the analysis procedures for the primary efficacy endpoint.

• If the test for normality fails for percent change from baseline at α level of 0.10 but not change from baseline, change from baseline will be used as the primary endpoint;

• If the test for normality fails for both percent change and change from baseline at α level of 0.10, percent change from baseline will be used as the primary endpoint, but non-parametric methodology will be used for the primary endpoint analysis. The van Elteren's test will be applied to test the percent change from baseline endpoint.

The treatment effect based on the baseline complement profile of subjects may also be investigated.

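### SAP 5.3.1.3 tests the UPCR effect separately above and below 1 g/g and plans no treatment-by-subgroup contrast, so the results cannot show whether the effect differs between the subgroups.

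*SAP*

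**What the plan says.** SAP 5.3.1.3 sets the UPCR subgroups at baseline above 1 versus at most 1 g/g: "A subgroup analysis will be carried out separately based on baseline UPCR". It then refers back to the main analysis: "These analyses will be the same as described in Section 5.3.1.1 for the following". Two populations follow, the elevated C5b-9 stratum and the combined strata.

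The model in SAP 5.3.1.1 is "model LR2BASE = TRT01AN VISITN TRT01AN*VISITN LBASE". It contains treatment, visit, their interaction and baseline, and no subgroup term. The code requests "lsmeans VISITN*TRT01AN / alpha=0.05 cl pdiff slice=VISITN", and the text adds: "Corresponding P-values will also be presented". Protocol 8.7 sets all testing at two-sided 0.05. The sequential testing in SAP 3.1 covers only the activity index and then the chronicity index. UPCR and its subgroups lie outside it.

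Two other places touch on subgroups, in weaker terms:

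- **eGFR (SAP 5.3.2).** An analysis of change and percent change, split at 60 mL/min/1.73 m², "will be performed in patients with impaired renal function at baseline eGFR", provided the subgroups are large enough.
- **Histology (SAP 5.2).** "The heterogeneity of the treatment effect across disease diagnoses and renal transplant strata may be investigated through subgroup analyses". Protocol 8.7.5 has the firmer "The heterogeneity of the treatment effect across disease diagnoses and renal transplant strata will be investigated through subgroup analyses", but the SAP states that it supersedes the protocol on statistical methods.

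SAP 5.1 and Protocol 8.7.7 allow covariate or subgroup analyses (the protocol also stratified ones) and name no interaction test. The only interaction in either document is treatment by visit.

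**The concern.** A reader given a p-value below 0.05 in one UPCR subgroup and above 0.05 in the other will tend to conclude that the drug works in the first and not in the second. That conclusion needs an estimate of the difference between the two effects, and the plan produces none. Each subgroup is smaller than the whole, so its test has less power, and the smaller subgroup fails more often for that reason alone. A uniform effect can then look selective.

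Repeating the analysis in the combined strata gives little protection. The elevated stratum is part of the combined population, so agreement between the two is not independent support.

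The SAP also gives UPCR more weight than the protocol did. Protocol 8.3.2 lists it among the other efficacy endpoints, whereas SAP 2.3.2 lists it first among the secondary endpoints. The subgroup results carry no exploratory label and no rule for reading them.

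**Working it through.** **Inputs**

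- 22 patients per arm in a stratum (Protocol 8.8, SAP 9).
- Two-sided alpha 0.05 (Protocol 8.7; SAP 5.3.1.1 code).
- Histology only: difference 35, SD 34, so d = 35/34 = 1.03.
- UPCR effect size: not documented. Assumed values are d = 0.3, 0.4, 0.59 and 1.03; the last is borrowed from histology.
- Share of patients above 1 g/g: not documented. Assumed 11:11 and 15:7 per arm.
- A t-test at one time point stands in for the repeated-measures model.

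**Step 1: the plan's own figure.** For n per arm, the noncentrality is d × √(n/2) with 2n − 2 degrees of freedom. At n = 22: 1.029 × √11 = 3.41, power 91.5%. At n = 21 power is 90.2%. The stated 22 per arm for 90% power is reproduced.

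**Step 2: power in a subgroup of m per arm, same true effect.** Noncentrality d × √(m/2), 2m − 2 degrees of freedom. For d = 1.03:

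- m = 11: noncentrality 2.41, critical value 2.09, power 0.632.
- m = 15: 2.82, 2.05, power 0.777.
- m = 7: 1.93, 2.18, power 0.425.

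**Step 3: significant in exactly one subgroup.** The subgroups share no patients, so P = p1(1 − p2) + p2(1 − p1).

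- 11:11: 2 × 0.632 × 0.368 = 0.465. Both are significant in 0.632² = 0.40.
- 15:7: 0.777 × 0.575 + 0.425 × 0.223 = 0.54. The first product, 0.447, is the larger subgroup alone; the second, 0.095, is the smaller alone. Size largely decides which subgroup appears to respond.

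| Assumed d | Overall power, 22 per arm | Exactly one, 11:11 | Exactly one, 15:7 |
|---|---|---|---|
| 0.30 | 16% | 18.5% | 18.6% |
| 0.40 | 25% | 24.8% | 25.2% |
| 0.59 | 48% | 38.6% | 39.9% |
| 1.03 | 91.5% | 46.5% | 54.1% |

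**Step 4: no effect at all.** At least one of two tests significant: 1 − 0.95² = 0.0975. Exactly one: 2 × 0.05 × 0.95 = 0.095.

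**Step 5: what a contrast would add.** In simulations of 40,000 trials per setting with a uniform effect (overall power 50% to 92%), a treatment-by-subgroup test at 0.05 wrongly declared a difference in 4.8% to 5.1%. Among trials significant in exactly one subgroup, only about 7% to 12% had an interaction p-value below 0.05.

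**Step 6: how precise the contrast is.** Its standard error is SD × √(2/m1 + 2/m2).

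- 11:11: √(2/11 + 2/11) = 0.603 SD, against √(2/22) = 0.302 SD for the overall effect. The 95% half-width is 2.02 × 0.603 = 1.22 SD.
- 15:7: standard error 0.647 SD, half-width 1.31 SD.
- Take an interaction as large as the overall effect, with overall power 90% and equal subgroups. By normal approximation the standardised contrast is (1.96 + 1.28)/2 = 1.62, so power is about 37%. At 80% overall power it is about 29%.

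**The case against.** The strongest reply is that nothing depends on these analyses. UPCR is outside the sequential testing, this is a Phase 2 trial, no decision rule uses the subgroups, and the SAP never says that subgroup p-values will be compared. SAP 5.3.1.3 sets no heterogeneity question; that wording belongs to histology. A within-subgroup estimate is a legitimate description of that subgroup. All of this stands, and it limits the point to a risk of misreading.

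The size also depends on undocumented inputs. At d = 0.3 to 0.4 the split result occurs in about a fifth to a quarter of trials, not half. The planned model uses several visits, and its restriction to baseline UPCR of at least 0.15 g/g may make the subgroups smaller than assumed. That stands too, so the results are given as a range.

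The remedy has limits. A joint model with all visit interactions has 2 × 2 × 6 = 24 treatment-by-subgroup-by-visit means over the six post-baseline visits in SAP 5.3.1, in about 44 patients. It would also impose a common covariance unless that is modelled by subgroup. The contrast does nothing about false positives within a subgroup when there is no effect; the exploratory label addresses those.

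What the reply does not remove is that the plan prints two p-values side by side and gives no estimate of their difference.

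A reader might also infer that the eGFR and histology subgroups have the same defect. The documents do not go that far. SAP 5.3.2 is conditional on numbers, does not say the fits are separate, and carries over only UPCR's primary and secondary analyses. SAP 5.2 is optional and specifies no subgroup model, so an interaction term is not excluded.

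**Conclusion.** The point holds for UPCR as a minor matter of analysis choice. The planned separate tests cannot show whether the effect differs by baseline proteinuria. How often a uniform effect would look selective runs from about 19% to 54% over the assumed effects and splits, with 9.75% for at least one significant subgroup when there is no effect. These figures assume 22 per arm, a single-time-point t-test and the same true effect in both subgroups.

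Two stronger readings are not supported. First, type I error for the primary endpoint is not inflated, because these tests play no part in the primary claim. Second, one could add the eGFR subgroups on both scales and reach a chance of some false positive of about 0.21 in the elevated stratum, or 0.29 to 0.33 with the combined strata. Those figures require the conditional eGFR analyses to be run as separate tests, and they rest on assumed correlations (0.5 between endpoints, 0.9 between the two eGFR scales). They should not be quoted as properties of the plan.

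**What to change.** In SAP 5.3.1.3:

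- Report the treatment-by-subgroup contrast for UPCR with its 95% CI. Take it from one repeated-measures model with subgroup, treatment-by-subgroup and the related visit interactions. If that model does not converge, use the difference between the two separate subgroup estimates, with standard error √(SE1² + SE2²).
- Show each subgroup estimate with its CI and label all of them exploratory.
- State that no subgroup claim will rest on a within-subgroup p-value.

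Apply the same rule in SAP 5.3.2 if the eGFR subgroups are run, and in SAP 5.2 for disease type and transplant if heterogeneity is investigated and cell counts allow.

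The cost is a few sentences and several extra model terms. No new data are needed and the primary analysis does not change. The downside is an imprecise contrast with about 44 patients. Showing its CI is preferable to leaving that imprecision hidden behind two p-values.
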